5.6. Rescue Therapy

A rescue treatment is defined as any procedure or medication (new medications or medications that have been increased in dose) used for the treatment of new or persistent symptoms of UC.

If a subject who does not exhibit a clinical response experiences worsening of disease (ie, worsening of clinical status or symptoms of UC that require rescue treatment) or disease relapse, study drug must be discontinued, and subjects should be treated as clinically appropriate with conventional treatments for active disease, as determined by the investigator. These subjects should continue in the study for safety assessments but will be considered treatment failures with respect to the intent-to-treat population.

A subject will be considered to have disease relapse when they meet all of the following criteria:

- an increase in UC disease activity after achievement of a clinical response, defined as an increase from nadir or Day 57 in partial Mayo score of ≥ 2 points and an absolute partial Mayo score ≥ 4 points, and
- an endoscopic subscore of ≥ 2 points, and
- exclusion of other causes of increased disease activity that are unrelated to UC (eg, infections or changes in medication).

The date and time of rescue medication administration as well as the name and dosage regimen of the rescue medication must be recorded.

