Concomitant medication		X	
Subject diary completion		X	
Study drug			
Study drug administration		X	
Compliance review	X	X	X
Safety			
Urine pregnancy test ^b		X	X
Chemistry, haematology, coagulation, and urinalysis		X	X
Vital signs		X	X
12-lead ECGs		X	X
Physical examination		X	X
Adverse event monitoring		X	
Endoscopic and clinical assessments			
UCEIS			X ^d
Total Mayo score ^c			X ^d
Partial Mayo score ^{c,e}		X	X
Modified Mayo score ^{c,f}			X ^d
Health-related quality of life			
IBD questionnaire		X	X
Biomarkers			
C-reactive protein		X	X
Faecal calprotectin		X	X
Endoscopy/biopsy			
Endoscopy			X ^g
Histopathology			X ^d

Abbreviations: d = days; ECG = electrocardiogram; EOS = end of study; ET = early termination; IBD = inflammatory bowel disease; UCEIS = Ulcerative Colitis Endoscopic Index of Severity.

a Telephone visit; however, at the discretion of the investigator, subjects may be requested to attend the study site for safety assessments.

b Females only.

c Mayo scores collected from 1 week prior to each visit (including endoscopy visit).

d If endoscopy is performed.

e Rectal bleeding, stool frequency, and Physician's global assessment.

f Rectal bleeding, stool frequency, and findings on endoscopy.

g Endoscopy performed at the discretion of the investigator. If an endoscopy is performed, it should be performed ≤ 7 days prior to the EOS/ET visit or on the same day as the other EOS/ET procedures/assessments.

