5.2 Handling of Dropouts, Missing Data, and Outliers

For the primary and secondary efficacy responder analysis based on the total Mayo score, subjects with missing data will be deemed as "unresponsive". For subjects who received rescue therapy after the first dose of study drug and prior to Day 57, the response status will be deemed as "unresponsive" regardless of the Mayo score value at Day 57.

In terms of the exploratory endpoints, for the endoscopic response rate by total Mayo score, if a subject has no Mayo endoscopic subscore on Day 57, then the last post-baseline measurement prior to Day 57 will be used and the analysis will be based on the imputed value. If a subject does not have any post-baseline Mayo endoscopic subscore measurement, then the subject will be deemed as "unresponsive".

For modified Mayo remission rate at Day 57, if a subject has more than or equal to 2 questions are not answered, then the subject will be considered as "unresponsive". If a subject has only 1 question is not answered, then the last post-baseline question answered prior to Day 57 will be used to calculate the modified Mayo remission rate at Day 57.

For systemic remission rate at Day 57 based by total Mayo score, if a subject has 2 questions are not answered, then the subject will be considered as "unresponsive". If a subject has only 1 question is not answered, then the last post-baseline question answered prior to Day 57 will be used to calculate the systemic remission rate at Day 57.

For the clinical remission at Day 112, the percentage of subjects with sustained remission on Day 112, and the clinical response rate at Day 112 which are all based on the total Mayo score, if a subject has more than or equal to 3 questions are not answered, then the subject will be considered as "unresponsive". If a subject has less than 3 questions are not answered, then the last post-baseline question(s) answered prior to Day 112 will be used to calculate the total Mayo score and information relevant to derive those Day 112 related exploratory endpoints.

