6.4.4.1 Rescue Medication

Rescue medication will be coded by Labcorp using the WHODrug Dictionary [Version Sep2020 B3 (or a later version if updated during the study)], ATC Classification codes.

The number and percentage of subjects using each therapy will be displayed together with the number and percentage of subjects using at least 1 medication within each therapeutic class (ATC-Level 2), chemical subgroup (ATC-Level 4), and generic term for each phase and by treatment group for the Safety Population.

Statistical Analysis Plan

Sponsor Name: Bridge Biotherapeutics, Inc.
Sponsor Protocol ID: BBT401-UC-005

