6.4.4.2 Rescue Procedure

Rescue procedure will be coded by Labcorp using the Medical Dictionary for Regulatory Activities (MedDRA) [Version 23.1 (or a later version if updated during the study)].

The number and percentage of subjects with any rescue procedure will be summarised by system organ class (SOC) and preferred term (PT) for each phase and by treatment group for the Safety Population.

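### SAP 5.2 has no rescue or relapse override at Day 112, so a subject Protocol 5.6 calls a treatment failure can be counted as a Day 112 responder or remitter

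*SAP*

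**What the plan says.** **Protocol 5.6 (Rescue Therapy).** The failure condition opens "If a subject who does not exhibit a clinical response experiences worsening of disease", requires that the worsening need rescue treatment, and adds disease relapse as an alternative. Study drug stops, and then: "These subjects should continue in the study for safety assessments but will be considered treatment failures with respect to the intent-to-treat population". No day limit is given. Relapse presupposes an earlier clinical response and is "defined as an increase from nadir or Day 57 in partial Mayo score of" at least 2 points, with a partial Mayo score of at least 4, an endoscopic subscore of at least 2, and other causes excluded. Since Day 57 is a reference point, the rule reaches into the extension phase.

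**SAP 5.2.** The rescue rule sits in the paragraph on the primary and secondary responder analyses: "For subjects who received rescue therapy after the first dose of study drug and prior to Day 57, the response status will be deemed" unresponsive, whatever the Day 57 Mayo score. The separate Day 112 paragraph makes a subject unresponsive only if three or more questions are unanswered. Otherwise "the last post-baseline question(s) answered prior to Day 112 will be used to calculate the total Mayo score". It mentions neither rescue nor relapse.

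**SAP 6.6.5** derives Day 112 remission and sustained remission from Mayo scores alone. All three Day 112 endpoints are analysed in the ITT population with exact confidence intervals and Fisher tests.

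**SAP 6.4.4** anticipates rescue in both phases but only tabulates it: medication by "generic term for each phase and by treatment group for the Safety Population", procedures by "preferred term (PT) for each phase and by treatment group for the Safety Population".

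**Protocol Appendix 11** schedules the partial Mayo score at Day 112 but not the endoscopy: "Endoscopy performed at the discretion of the investigator".

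**The concern.** The two documents classify the same subject differently. The protocol names the ITT population and calls the subject a failure. The SAP analyses that population at Day 112 from scores that may have been obtained after conventional treatment replaced study drug. Symptom relief from rescue could then be tabulated as durability on study drug, with an interval and a p-value attached.

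Nothing else visible in the SAP would reveal this. The stated scope of the sensitivity analyses in SAP 6.6.3 is Day 57 response and Day 57 remission. SAP section 7 declares no departure from Protocol 5.6.

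There is also a mismatch of triggers. The SAP's Day 57 rule counts any rescue but not relapse, while the protocol counts relapse but not every rescue. The exploratory Day 57 responder endpoints carry no visible rescue rule at all.

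**Working it through.** The documents give no figure to reproduce, so the check asks whether the SAP's rules can classify a protocol failure as a success, and what one such subject weighs.

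**Inputs.** Scores are written stool + bleeding + PGA + endoscopy, each 0 to 3. Response is a fall of at least 3 points and at least 30%, with bleeding down by at least 1 or at most 1. Remission is a total of at most 2 with no subscore above 1. A question in the SAP 5.2 Day 112 paragraph is taken to be a Mayo subscore, so a missing endoscopy is one unanswered question and triggers carry-forward. All example scores are assumed.

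**A. Rescued non-responder, endoscopy carried forward**
- Baseline 2+2+2+3 = 9; Day 57 2+2+2+3 = 9, not a responder.
- Worsening and rescue in the extension; no Day 112 endoscopy.
- Day 112: 1+1+1 + carried 3 = 6. Fall 3, 3/9 = 33.3%, bleeding 1: SAP response.

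**B. Rescued non-responder with a low Day 57 endoscopic subscore**
- Baseline 2+2+2+2 = 8; Day 57 2+2+2+1 = 7, not a responder.
- Worsening and rescue; no Day 112 endoscopy.
- Day 112: 1+0+0 + carried 1 = 2. Fall 6, 6/8 = 75%, no subscore above 1: SAP response and remission.

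**C. Relapse, no carry-forward**
- Baseline 3+2+2+3 = 10; Day 57 1+0+1+2 = 4, a responder with partial Mayo 2.
- Day 112 observed: 2+1+1+2 = 6. Partial Mayo 4, a rise of 2, endoscopy 2: relapse thresholds met if other causes are excluded.
- Fall 4, 4/10 = 40%, bleeding 1: SAP response on the same scores.

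**How wide the routes are**
- *Allowed baselines.* Inclusion criterion 3 requires stool and bleeding of at least 1, endoscopy of at least 2 and a total of at least 6. That gives 3 × 3 × 4 × 2 = 72 combinations, less 5 with totals 4 or 5, so 67. By total: 6: 9; 7: 14; 8: 16; 9: 14; 10: 9; 11: 4; 12: 1.
- *Relapse with response.* The lowest total at relapse is 4 + 2 = 6, so a 3-point fall needs a baseline of 9 or more: 14 + 9 + 4 + 1 = 28 baselines, each with at least one such path. The other 9 + 14 + 16 = 39 have none.
- *Remission with carried endoscopy.* Of 4³ = 64 diary/PGA combinations, a carried 0 allows 7 (items 0 or 1, sum at most 2: 8 − 1). A carried 1 allows 4 (sum at most 1: 1 + 3). A carried 2 or 3 allows none.

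These counts show what is possible, not how often it would occur.

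**Weight of one subject.** With 12 per randomised arm, 1/12 = 8.3 percentage points. Clopper-Pearson 95% intervals, counts assumed:

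| Endpoint | Protocol classification | With one failure counted as success |
|---|---|---|
| Response | 3/12 = 25.0% (5.5 to 57.2) | 4/12 = 33.3% (9.9 to 65.1) |
| Remission | 0/12 = 0% (0 to 26.5) | 1/12 = 8.3% (0.2 to 38.5) |

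If Day 112 groups are formed by treatment received in the extension, the BID group could reach 12 + 12 = 24 and one subject would weigh 1/24 = 4.2 points.

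**The case against.** The strongest reply is that this is silence rather than contradiction. The SAP is based on the protocol and declares no departure from 5.6, so the failure rule could be said to apply by default. But the SAP wrote an explicit override for Day 57 and none for Day 112, and a programmer working from 5.2 and 6.6.5 would not apply one. Redaction does not explain the gap, because the Day 112 text in both sections is fully visible.

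Several narrower points stand:

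- **Remission after relapse is hard to reach.** Relapse needs an endoscopic subscore of at least 2. If that value is the last recorded, it is the one carried forward and rules out remission, so a later subscore of 0 or 1 is needed.
- **Sustained remission is narrower still.** A Day 57 remitter falls from at least 6 to at most 2 with bleeding at most 1, so is always a responder. Such a subject becomes a protocol failure only through relapse.
- **Data may not exist.** Failures stay in the study for safety assessments. If three or more Mayo items are not collected at Day 112, SAP 5.2 already gives unresponsive.
- **Protocol 5.6 is loosely worded.** Its sentence begins with a non-responder yet includes relapse, which requires prior response. Treating these as two groups is the only reading consistent with the relapse definition.
- **The consequence is limited.** The endpoints are exploratory, Protocol 8.4.2 tests no formal hypothesis on them, and placebo and QD non-remitters change treatment after Day 57, so Day 112 contrasts are not clean randomised comparisons.

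These points limit how often the problem could arise and how much rests on it. They do not remove it: routes A to C remain open.

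**Conclusion.** The concern holds. SAP 5.2 and 6.6.5, followed as written, can report a Protocol 5.6 treatment failure as a Day 112 responder, and as a remitter when the endoscopic subscore used is 0 or 1. Route C shows that changing the carry-forward rule alone would not close the gap.

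The conclusion rests on the two-group reading of 5.6 and on Mayo items being collected at Day 112 after failure. The size cannot be fixed from the documents beyond the weight per subject: 8.3 points at 12 per group, 4.2 at 24. This should be corrected before analysis, although it affects exploratory durability evidence rather than the primary result.

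**What to change.** Leave the existing Day 57 rule unchanged and amend SAP 5.2 as follows.

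1. Add to the Day 112 paragraph: *Subjects who received rescue therapy, or who met the Protocol 5.6 treatment-failure condition including relapse, after first dose and before or at the Day 112 assessment are unresponsive for Day 112 clinical response, clinical remission and sustained remission. This takes precedence over carry-forward.*
2. Apply the existing pre-Day 57 rescue rule to the exploratory Day 57 responder endpoints.
3. Reconcile the SAP and protocol wording of the trigger without narrowing the Day 57 rule. The clinical definitions in Protocol 5.6 are not at issue.

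The cost is SAP wording and programming. Protocol 5.6 already requires rescue medication dates to be recorded. A relapse flag also needs the investigator's exclusion of other causes, so check that the CRF captures it. Day 112 rates may be slightly less favourable. An earlier responder rescued without confirmed relapse would also become unresponsive; 5.6 does not require this, but it matches the SAP's own Day 57 standard.

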8.4.2. Exploratory Efficacy Analysis

All subjects in the intent-to-treat population will be included in the exploratory efficacy analysis. The estimate and 95% CI of endoscopic response rate and histological improvement at Day 57, and clinical response rate and the percentage of subjects with clinical remission at

Day 112 will be calculated using the exact binomial method for each treatment. Actual values and change from baseline in Mayo scores, UCEIS scores, IBDQ total score, C-reactive protein, and faecal calprotectin over time will be summarised descriptively. No formal hypothesis will be tested on the exploratory efficacy endpoints.

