6.6.3 Sensitivity Analysis

The following sensitivity analysis will be performed on the primary efficacy endpoint (the clinical response rate at Day 57) and the first secondary efficacy endpoint (the clinical remission rate at Day 57).

For these analyses, the following rules will apply.

[REDACTED]

[REDACTED]

[REDACTED]

[REDACTED]

In addition, the primary efficacy analysis will also be performed for the per-protocol population.

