- **Clinical remission at Day 112, as measured by a total Mayo score of ≤ 2 points, with no individual subscore exceeding 1 point.**

Total Mayo Score will be evaluated. Subjects who have a total Mayo score ≤ 2 points, with no individual subscore exceeding 1 point at Day 112, will be considered as achieving clinical remission.

The number and proportion of subjects with the 95% CI of clinical remission rate at Day 112 will be calculated using the exact binomial method for each treatment. The Fisher's exact test will be used to evaluate any differences between treatments at Day 112 for the extension phase by treatment group for the ITT Population.

- **Sustained remission at Day 112.**

Total Mayo Score will be evaluated. Subjects who have a total Mayo score ≤ 2 points, with no individual subscore exceeding 1 point at day 57 and day 112 will be considered as achieving sustained remission at day 112.

The number and proportion of subjects with the 95% CI of sustained remission at Day 112 will be calculated using the exact binomial method for each treatment.

Statistical Analysis Plan

Sponsor Name: Bridge Biotherapeutics, Inc.
Sponsor Protocol ID: BBT401-UC-005

The Fisher's exact test will be used to evaluate any differences between treatments at Day 112 for the extension phase by treatment group for the ITT Population.

- **Clinical response rate at Day 112.**

The number and proportion of subjects with the 95% CI of clinical response rate at Day 112 will be calculated using the exact binomial method for each treatment. The Fisher's exact test will be used to evaluate any differences between treatments at Day 112 for the extension phase by treatment group for the ITT Population.

- **Change from baseline to Day 57 in the Partial Mayo score.**

Mixed Model Repeated Measures (MMRM), with repeated change from baseline values as the dependent variable and baseline values as the covariate variable, will be used to compare the change from baseline to Day 29 and 57 in the partial Mayo score between treatment and placebo group. The sample SAS code is provided in Appendix 2. The 95% CI for the difference in the change from baseline will be calculated for each treatment, and the p-value will be provided.

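### The SAP's rescue rule stops at Day 57, so a subject rescued later whom Protocol 5.6 calls a treatment failure can be scored a Day 112 responder

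*SAP*

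**What the plan says.** **Protocol 5.6 (Rescue Therapy).** The rule begins "If a subject who does not exhibit a clinical response experiences worsening of disease" and goes on to name disease relapse as well. In either event study drug stops. The subject stays in the study for safety assessments, and these subjects "will be considered treatment failures with respect to the intent-to-treat population". No time limit is given. Relapse requires all of the following: a rise in partial Mayo score measured from nadir or Day 57, an endoscopic subscore of at least 2, and exclusion of causes unrelated to UC.

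**SAP 5.2, Day 57.** The rescue rule sits in the paragraph on the primary and secondary responder analyses. It opens "For subjects who received rescue therapy after the first dose of study drug and prior to Day 57" and overrides the Day 57 Mayo score.

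**SAP 5.2, Day 112.** For clinical response, clinical remission and sustained remission there is only a missing-item rule. Three or more missing Mayo items means unresponsive. With fewer missing, each gap is filled by that item's latest post-baseline answer before Day 112. Rescue is not mentioned.

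**SAP 6.6.5.** Remission at Day 112 is defined by score alone. Subjects who meet the score criterion at both Day 57 and Day 112 "will be considered as achieving sustained remission at day 112". Day 112 clinical response has no derivation of its own and no rescue condition. The SAP names Fisher's test for each of these endpoints, which "will be used to evaluate any differences between treatments at Day 112 for the extension phase by treatment group for the ITT Population".

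**Protocol 8.4.2.** "All subjects in the intent-to-treat population will be included in the exploratory efficacy analysis". This is the population in which Protocol 5.6 declares failure. The same section tests no formal hypothesis on these endpoints.

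**The concern.** At Day 57 the plan lets rescue override the Mayo score, so that improvement due to another drug is not credited to BBT-401-1S. The same reasoning applies at Day 112, and relapse after Day 57 can occur only in that later period. As the SAP is written, the override is not carried forward. A subject can stop study drug, receive conventional treatment for active disease, improve on it, and enter the Day 112 numerator. Part of a Day 112 rate could then reflect the rescue treatment, and the reported result would disagree with the subject's status under Protocol 5.6.

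**Working it through.** The plan gives no figure to reproduce here. The check applies the written rules to an illustrative subject and then sizes one misclassification.

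**Inputs from the documents**
- Response: total Mayo falls by at least 3 points and at least 30%, and rectal bleeding falls by at least 1 point or is at most 1 (SAP 3.1; Protocol 2.2.1).
- Remission: total at most 2, no subscore above 1 (SAP 3.2 and 3.3).
- Entry: total at least 6, rectal bleeding at least 1, endoscopic subscore at least 2 (Protocol 4.1).
- Extension entry is offered to all who complete induction, with no response requirement (Protocol 3.1).
- Partial Mayo is scheduled at Day 112; endoscopy is at the investigator's discretion (Protocol Appendix 11).
- Planned arm size is 12 (Protocol 3.1).

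**Step 1: worked subject** (assumed scores, in the order stool + bleeding + PGA + endoscopy)
- Baseline: 2+2+2+2 = 8.
- Day 57: 2+2+2+2 = 8. The fall is 0, so a non-responder, who enters the extension.
- The subject worsens, needs rescue and stops study drug. Protocol 5.6: treatment failure.
- Day 112: 1+1+1+2 = 5. The fall is 8 − 5 = 3 points; 3/8 = 37.5%; bleeding goes from 2 to 1. SAP: clinical response.

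The endoscopic subscore of 2 may be read at Day 112 or carried forward from Day 57. The total is 5 either way, so the result does not depend on carry-forward.

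**Step 2: how much improvement is needed**
- For baseline totals 6 to 10, a 3-point fall is 3/6 = 50.0% down to 3/10 = 30.0%, which meets both thresholds. One point each on stool, bleeding and PGA is enough with endoscopy unchanged.
- For baselines 11 and 12, 4 points are needed: 4/11 = 36.4% and 4/12 = 33.3%.

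**Step 3: remission and sustained remission**
- A Day 57 non-responder cannot reach sustained remission. Day 57 remission from a baseline of at least 6 is a fall of at least 6 − 2 = 4 points (at least 4/6 = 66.7%) with bleeding at most 1, so it implies response.
- Day 112 remission in such a subject is possible. It needs an endoscopic subscore of 0 or 1 (read or carried forward) and a total of at most 2, which asks far more than response.
- A subject with protocol-defined relapse has a recorded endoscopic subscore of at least 2. If carried forward, it blocks remission. Remission, sustained or not, then needs a later endoscopy scoring 0 or 1 by Day 112.

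**Step 4: size of one subject**
- 1/12 = 8.3 percentage points.
- Assumed counts, exact 95% CI: 3/12 = 25.0% (5.5 to 57.2) becomes 4/12 = 33.3% (9.9 to 65.1).
- SAP 6.1 uses the analysis population as denominator unless table shells differ. If shells counted only extension entrants, with 8 or 6 assumed per arm, one subject would be 1/8 = 12.5 or 1/6 = 16.7 points.
- Fisher's exact test, assumed counts: 5/12 vs 0/12 gives p = 0.037. With one of the five reclassified as a failure, 4/12 vs 0/12 gives p = 0.093.

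**The case against.** **Silence is not contradiction.** The SAP is written from the Protocol, and SAP section 7 lists no change to rescue handling, so Protocol 5.6 can be said still to govern. This is fair: the SAP nowhere says that a rescued subject counts as a responder. But its Day 112 derivation is complete without Protocol 5.6, and followed literally it returns a response in Step 1. A rule written out for Day 57 and omitted for Day 112 invites that reading.

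**Rescued subjects may have no Day 112 scores.** Protocol 5.6 retains them for safety assessments and does not say whether Mayo items continue. With three or more missing they are already unresponsive. This limits the number affected. It does not close the gap, because three of the four items are scheduled at the Day 112 visit.

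**Existing safeguards.** Rescue is tabulated by phase (SAP 6.4.4), so a reader could see that it occurred. The rules in SAP 6.6.3 are redacted, but their stated scope is the Day 57 response and remission rates. Neither applies rescue to a Day 112 endpoint.

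**A tempting stronger reading.** A reader might infer that every subject rescued in the extension is a treatment failure whom the SAP miscounts. Protocol 5.6 does not go that far. A remitter who flares and is rescued without an endoscopy has no recorded subscore of 2 or more. That subject does not meet the relapse definition and is not a non-responder. Counting that subject in sustained remission may be undesirable, but it does not conflict with the Protocol.

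**Conclusion.** The gap is real and minor. For the subjects Protocol 5.6 covers, the SAP's Day 112 rules can return a responder where the Protocol says treatment failure. The main exposure is Day 112 clinical response in a Day 57 non-responder. Clinical remission is less exposed, and sustained remission after a confirmed relapse requires a favourable later endoscopy.

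The size is 8.3 points per subject on a denominator of 12. How many subjects to expect cannot be derived from the documents; the counts and scores used above are assumptions. The conclusion also assumes that Protocol 5.6 names two separate triggers (worsening in a non-responder, and relapse). Its opening clause runs them together, although relapse is defined as following a response.

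A reader might infer that the trial's main efficacy result is at risk. It is not: SAP 5.2 already protects the Day 57 primary and secondary responder endpoints. The Day 112 endpoints are exploratory, and their Fisher p-values carry no formal hypothesis under Protocol 8.4.2. Nor is Day 112 a clean randomised comparison, since non-remitters on placebo and on QD change treatment after Day 57.

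**What to change.** Add one sentence to the Day 112 paragraph of SAP 5.2, for example: *Any subject given rescue therapy between the first dose and the Day 112 assessment is counted as not having achieved Day 112 clinical response, clinical remission or sustained remission, whatever the Day 112 Mayo score or any carried-forward value.*

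The SAP should say that this mirrors the Day 57 rule, which counts any rescue. It should also say that the rule goes slightly beyond Protocol 5.6, since it also fails responders who were rescued without meeting every relapse criterion.

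The cost is that sentence and its programming. Rescue medication and procedures are already recorded on the CRF (SAP 6.4.4), and no visit or endoscopy is added. Day 112 rates may come out slightly less favourable.
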